erect with feet together and head level; height will be measured to the nearest 0.5 cm. Weight will be measured to the nearest 0.25 lbs using a balanced scale. BM will be calculated as weight in kilograms divided by the square of the height in meter. Waist and hip circumferences will be measured in the standing position. The subject should be wearing unrestricting undergarments with a hospital gown being optional. Waist circumference will be measured at the level midway between the lateral lower rib margin and the iliac crest. Hip circumference will be measured at the level of the trochanters through the pubic symphysis.

v. Study Visits: Participants in both groups will meet with registered dietitians every 2 to 4 week throughout the Intervention Phase and the dietary intake patterns will be reviewed. A variety of visual tools including food models and common household measuring utensils will be used during the interview to help participants gauge amounts accurately.

a. Assessment will be performed at weeks 0, 2, 4, 6, 8, 12, 16.

1. Vital signs
2. Height
3. Weight
4. Vital Signs
5. Fasting Labs: CBC/Metabolic Panel, Hemoglobin alc, TSH, Cholesterol, TG, HDL, blood sugar, hormone panel (leptin, CCK, GLP-1, PYY, ghrelin, insulin, nesfatin-1)
6. Body Composition and estimated resting metabolic rate
7. Hepatic transient elastography
8. Stool collection for fecal short chain fatty acids and microbiome analysis
9. Satiety Scale
10. 3-Day food record
11. Food frequency questionnaire
12. Adverse Event Tracking

Compliance with consumption will be assessed using check lists that will be turned in during clinical visits. Minimal accepted compliance will be set at 80% of the assigned diet. A participant will be withdrawn once cumulative consumption levels fall to the point that 100% compliance cannot get them over the 80% threshold by the final day of the intervention.

Study Schedule

Procedures	Screen Week -1	Baseline Week 0	Week 2	Week 4	Week 6	Week 8	Week 12	Week 16
Informed Consent	X							
Medical History	X							
Physical Examination	X							
Labs: Serum Pregnancy Test (if needed)	X							
Urine Pregnancy Test (if needed)	X							
Height		X	X	X	X	X	X	X
Weight		X	X	X	X	X	X	X
Vital Signs		X	X	X	X	X	X	X
Labs: CBC/Metabolic Panel, Hormones,		X	X	X	X	X	X	X

Hemoglobin a1c, TSH, lipids							
Body Composition BIA		X	X	X	X	X	X
Liver Stiffness Fibroscan		X	X	X	X	X	X
Product Dispensing		X	X	X	X	X	X
Stool collection		X	X	X	X	X	X
Satiety Scale		X	X	X	X	X	X

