Satiety Questionnaire: Satiety will be measured by using a visual analog scale. Participants will be asked to rate the degree to which they felt hungry by placing a mark on a visual analog scale numbered 0 to 10 (0 indicating "not hungry at all" and 10 indicating "as hungry as I have ever felt"). Participants will complete the scales at baseline and weeks 2, 4, 6, 8, 12 and 16.

Dietary Interventions: All participants will receive individual consultation on their respective diet plans, lifestyle modification, and physical activity with a registered dietitian or healthcare provider (i.e. nurse practitioner or physician) throughout the study. At the initial visit patient will not be calorie restricted but will have standardization of their nutritional macronutrient intake based on their group randomization. At the 2 week visit patient will then begin a 1500

calorie restricted diet with the same macronutrient composition (i.e. 30% protein and 40% carbohydrate, and 15% protein and 55% carbohydrate respectively for the high and standard protein groups). Participants in the high protein groups will receive a diet plan based on 1 gram of protein per pound of lean body mass, while the standard protein group will receive 0.5 gram of protein per pound of lean body mass. All subjects will be given guidelines to balance the rest of their caloric and nutritional needs with fruits, vegetables, and whole grains. All participants will meet with a dietitian or healthcare provider at baseline and weeks 2, 4, 6, 8, 12 and 16. Participants will also be weighed at each of these visits and will pick up meal replacement products at that time. All participants will be advised to keep self-monitoring daily food diaries to help with diet compliance and behavior change. Subjects will also be asked to complete the visual analog scale to assess fullness with the overall diet at the same time the 3DFR is being kept. Adherence with strict dietary controls will be performed by reviewing daily patient logs and telephone calls.

vii. Laboratory Studies: Blood samples will be obtained by venipuncture. Subjects will be required to fast at least 8 h and not more than 14 h prior to venipuncture. The laboratory tests will consist of the following: Chemistry Panel, Complete Blood Count (CBC), HbAl c, Lipid Panel, Liver Function Panel, Thyroid Stimulating Hormone (TSH) and C-Reactive Protein (CRP) performed by the laboratory.

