Stool samples will be collected on day 3, 7, 14, 17, 21, 28, 42, 56, 84 and 112. Subjects will be provided with kits for home sampling. The subjects will urinate first then defecate into the Fisherbrand Commode Specimen Collection System. Subjects will use a spoon to transfer freshly defecated feces to a Para-Pak stool collection cup prefilled with 95% ethanol to fix the samples, allowing storage at room temperature for up to 2 weeks. The remaining feces will be frozen. This involves removing the cup from the toilet hat, tightly closing the lid, and transferring the cup to a Ziploc bag for storage in the subject's freezer. Frozen samples will be delivered to the VA clinic during scheduled study visits using a Styrofoam box and frozen packs. Subjects who forget to bring samples will be provided with prepaid envelopes to mail their samples to the coordinator. Samples will be stored at -80°C. Ethanol-fixed and fresh frozen samples give comparable metagenomics results to samples stored in preservatives such as RNALater while minimizing subjects' risk of exposure to toxic chemicals ⁽³³⁾.

Statistical Analysis:

Statistical Design: This is a 2-group randomized nutritional study to evaluate whether the high-protein diet will improve weight loss in comparison to a standard (control) diet. Eligible subjects will be randomly assigned into one of the two groups in a ratio of 1:1.

Sample Size Determination: The sample size is determined based on the Specific Aim 1 to significantly improve weight loss, as observed by comparing the high-protein diet to the standard diet. The primary outcome of interest is weight loss at 16 weeks (the end of the study). An evaluable sample size of at least 165 (i.e., 55 per arm) will achieve 80% power to detect an effect size of 0.245 using an F test with a two-sided 0.05 significance level when comparing each of the two high-protein diets to the standard diet, assuming that the mean weight loss for the standard diet is 14 lbs with the common standard deviation within group of 10 (from preliminary data), and the size of the variation in the means is 2.45. To account for an attrition rate of up to 20%, we will enroll a total of 200 subjects (66 per arm). Preliminary data suggest that the estimated effect size ranges from 0.23-0.34 when comparing the high-protein diet to the standard diet.

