Data Analysis: Descriptive statistics (mean, standard deviation, median, inter-quartile range, and frequency distribution) of demographic information and baseline assessments will be generated to characterize the study participants. Patient characteristics and baseline measurements of the three diet groups will be compared using analysis of variance (ANOVA) for continuous variables, and Chi-square test for categorical variables to evaluate the appropriateness of the randomization. If the distribution of the variable is skewed, an appropriate variable transformation will be made before the comparison. Nonparametric methods, such as Kruskal-Wallis one-way analysis of variance, will also be used for comparison.

Primary Endpoint: the primary endpoint is change in body weight, which is calculated as the difference between Day 1 (baseline) and 16 weeks. The primary objective is to compare the weight loss between the high-protein diet and the standard diet. We will use ANOVA to compare the change in weight among the three groups (through contrast), and also use ANCOVA to compare the weight loss among these groups, adjusting for the baseline values and gender. If the primary endpoint is non-normally distributed, the Kruskal-Wallis one-way analysis of variance will be used.

Secondary Endpoints: The secondary endpoints are (1) efficacy variables: nutrition assessments (FFQ, 3DFR, and satiation questionnaire), anthropometric profiles (e.g., waist and hip circumferences), laboratory and biochemical variables (e.g., insulin, lipid levels, HbA1c), body composition (e.g., body fat), liver stiffness, microbiome changes, and level of hormones; (2) safety variables: incidence, severity and duration of adverse events, vital signs, concomitant medications and physical examination results.

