The Investigator must report to the occurrence of any *serious* adverse events, regardless of relationship to study product, or the first occurrence of any unexpected or previously unknown clinical event (regardless of Grade). A written report (Report for Serious/Life Threatening Events) of the event must be faxed within 5 working days to The VA GLAHS Institutional Review Board (IRB).

PREMATURE WITHDRAWAL OF PATIENTS

Whenever possible, patients will be studied for a minimum of 2 weeks. The patient's participation in the protocol will terminate under any of the following circumstances:

- At any time for any reason.
- Physician determination that patient's further participation in the protocol is not in the patient's best interest.
- At the determination of the sponsor.
- For any discontinuation, the investigator will obtain all the required details and document the date of and the reason for the discontinuation. If the reason for removing a patient is an AE, the specific event or the main laboratory abnormality will be recorded in the source.

**THE INVESTIGATOR WILL MAKE THOROUGH EFFORTS TO DOCUMENT THE OUTCOME
GOOD CLINICAL PRACTICES/ETHICAL CONSIDERATIONS**

This study will be conducted in accordance with Good Clinical Practices, Title 21 of the Code of Federal Regulations, Part 50, Subparts A and B; Part 56; and Part 312, Subpart D, and the 1996 International Conference of Harmonization (ICH) *Guideline on Good Clinical Practices*.

Data Collection

Source documents will be utilized for each patient entered into the study. Study participants will NOT be identified by name on any study documents. Patients will be identified by a patient identification number (PIN). Investigators will keep a patient code list accessible. All data collected will be stored in a secure locked file cabinet in accordance with the VA's Data Safety policies.

ETHICAL CONSIDERATIONS

The investigator will ensure that the study is conducted in full conformance with the FDA standards for human research as specified in 21 CFR 312.

Institutional Review Board (IRB)

The VA GLANS operates a Department of Health and Human Services-approved Institutional Review Board with a Federal Wide Assurance (FWA) agreement in place since the 2003 (FWAA00004642).

Institutional Review Board Approval

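### The 80% consumption rule removes participants after randomisation, with no later weight and no as-randomised analysis planned

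*Combined protocol and SAP*

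**What the plan says.** Randomisation follows screening (Aim 1, Procedures, Subject Eligibility). Compliance is judged during the intervention. Under Study Visits, "Compliance with consumption will be assessed using check lists that will be turned in during clinical visits", the minimum is 80% of the assigned diet, and "A participant will be withdrawn once cumulative consumption levels fall to the point that 100% compliance cannot get them over the 80% threshold"; that threshold is judged at the end of the intervention. Dietary Interventions adds that "Adherence with strict dietary controls will be performed by reviewing daily patient logs and telephone calls".

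The Premature Withdrawal section says that "participation in the protocol will terminate under any of the following circumstances", and then that "For any discontinuation, the investigator will obtain all the required details and document the date of and the reason for the discontinuation". A capitalised line follows: "THE INVESTIGATOR WILL MAKE THOROUGH EFFORTS TO DOCUMENT THE OUTCOME". It looks unfinished and names no outcome, weight or visit.

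Under Data Analysis, "the primary endpoint is change in body weight, which is calculated as the difference between Day 1 (baseline) and 16 weeks". The groups are compared by ANOVA, and also by ANCOVA adjusted for baseline and gender. The supplied text defines no intention-to-treat, as-randomised or per-protocol set and gives no rule for a missing week-16 weight. A mixed model (or GEE) for weight over time appears, but under Secondary Statistical Analyses.

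**The concern.** The trial asks whether a high-protein diet improves weight loss compared with a standard-protein diet. Randomisation protects that comparison only while the analysed groups remain the randomised groups. How much of the assigned diet a person eats is known only after randomisation, and the diet itself can influence it; satiety is part of the trial's own hypothesis.

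Ordinary dropout is largely outside the investigator's control. This loss is created by the protocol, and it includes people who would be willing to come back and be weighed. If the proportion withdrawn differs by arm, or if those withdrawn differ from the others by a different amount in each arm, the week-16 difference among those remaining is not the effect of assigning the diet. Weights that were never taken cannot be recovered at analysis.

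**Working it through.** **1. The plan's own sample size.** Sample Size Determination states: "An evaluable sample size of at least 165 (i.e., 55 per arm) will achieve 80% power to detect an effect size of 0.245". With three groups, noncentrality N × f² = 165 × 0.245² and alpha 0.05, power is 80.4%; at N = 162 it is 79.6%. The figure reproduces, but only as a three-group design. It is stated for evaluable participants, and Aim 2.1 likewise counts about 80 per group after a 20% dropout. Both fit the reading that people without week-16 data are not analysed. Neither defines the primary analysis set.

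**2. Whom the rule reaches.** Assume 112 equally weighted days from day 0. Allowed shortfall: 0.20 × 112 = 22.4 days. At day t the rule is met when cumulative consumption is below 1 − 22.4/t.

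| Visit | Day | Withdrawn if below |
|---|---|---|
| Week 4 | 28 | 20.0% |
| Week 6 | 42 | 46.7% |
| Week 8 | 56 | 60.0% |
| Week 12 | 84 | 73.3% |

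The rule cannot be met before about day 23, so every such withdrawal comes after randomisation. If counting starts at week 2, when calorie restriction begins (98 days, 19.6 allowed), it cannot be met at week 4, and the later cut-offs are 30%, 53% and 72%.

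Nor does the rule leave a clean at-least-80% set. On the 112-day count, steady consumers between 73% and 80% pass every visit check before week 16. Someone fully compliant to day 62 who then stops has missed 84 − 62 = 22 days at week 12, under 22.4, and finishes at 62/112 = 55.4%. Log reviews and telephone calls might catch some of these.

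**3. Bias if those withdrawn are left out.** Let p be the proportion withdrawn in an arm and g their shortfall in mean weight loss against those retained. The retained mean exceeds the all-randomised mean by g × p, so the bias in the high-minus-standard difference is gH·pH − gS·pS. It is zero when g and p are equal across arms.

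The documents give no withdrawal rate for this rule. The nearest figures come from the preliminary study of the same two protein levels (Work Accomplished, section B), which describes no compliance rule and covers all causes of missing data. Follow-up was available in 42 high-protein and 44 standard-protein participants.

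- With 50 per group (41 + 9 and 34 + 16): 1 − 42/50 = 16% against 1 − 44/50 = 12%, a gap of +4.0 points.
- With the stated randomised numbers (42 and 46): 0% against 1 − 44/46 = 4.3%, a gap of −4.3 points.

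With an assumed common shortfall of 6 to 12 lb, the bias in absolute size runs from 6 × 0.040 = 0.24 lb to 12 × 0.0435 = 0.52 lb. With no true difference, SD 10 and 80 per arm, SE = 10 × √(2/80) = 1.58 lb, and the two-sided 5% error becomes 5.3% and 6.2%.

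**The case against.** The strongest reply is that the key link is inferred. The compliance paragraph does not say whether withdrawal is from the diet or from the study, and the list of circumstances ending participation does not name non-compliance. Dietary Interventions has participants weighed at every visit to week 16, with no exception stated. The capitalised line may have been cut off in extraction, and Appendix 1 is not in the supplied text. An evaluable sample and an attrition allowance are routine. All this is why the conclusion says probably. If withdrawal from the diet only was meant, the protocol still needs to say so.

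Second, the mixed model can use weights taken before withdrawal, normally those at weeks 0, 2 and 4 at least. That stands as a partial check under a missing-at-random assumption. It is a secondary analysis and does not supply the missing week-16 weights.

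Third, the illustrated bias is small beside the SE, and its source is weak: the gap is two people (8 against 6 of 50, or 0 of 42 against 2 of 46), its sign depends on the denominator, and the preliminary study's counts do not agree with each other. Also, early checks catch only severe non-consumers, who may overlap with the 20% dropout already budgeted. These points stand. The illustration neither establishes a bias nor bounds it, because that study describes no such rule. No larger gap is claimed.

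**Conclusion.** The concern holds. The protocol orders withdrawal on a post-randomisation behaviour, plans no weight afterwards in the text available, and gives the primary week-16 analysis neither an as-randomised set nor a missing-data rule. Followed as written, it creates avoidable missing primary data that may be related to arm. That the primary comparison omits those withdrawn is a probable inference.

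The size and direction of any bias are not established. The 0.2 to 0.5 lb and 5.3% to 6.2% rest on an assumed 6 to 12 lb shortfall, equal in both arms, and a gap borrowed from another study. The visit cut-offs rest on equally weighted days and on when counting starts. This should be fixed, chiefly because it is cheap to prevent and cannot be repaired later.

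**What to change.** - **Follow-up.** In Study Visits and Premature Withdrawal, separate stopping the diet from leaving the study. For participants who do not withdraw consent, keep recording weight at the scheduled visits to week 16 whatever their compliance. Whether a non-compliant participant continues the diet is a clinical matter on which nothing is proposed here.
- **Primary analysis.** Under Data Analysis, include all randomised participants in their assigned arm. Use either the planned ANCOVA (baseline weight and sex) with a stated missing-data method, or the mixed model promoted to primary, with categorical time and the week-16 diet contrast.
- **Reporting.** Give withdrawals under the 80% rule by arm, and keep the at-least-80%-compliant set as a supportive analysis.

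The practical cost is wording in three sections and a few weighings at visits already scheduled. The statistical cost is that the as-randomised effect may be smaller. Suppose those withdrawn show no diet difference and the others show 4.9 lb with SD 10 (two-sided t test):

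| Withdrawn | As-randomised effect | Power, 100 per arm | Retained only, 4.9 lb |
|---|---|---|---|
| 10% | 0.9 × 4.9 = 4.41 lb | 87% | 90% (90 per arm) |
| 20% | 0.8 × 4.9 = 3.92 lb | 79% | 87% (80 per arm) |
| 30% | 0.7 × 4.9 = 3.43 lb | 68% | 82% (70 per arm) |

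The table assumes no ordinary dropout. If only 80 per arm are weighed at week 16, the first two as-randomised powers fall to 79% and 69%; the retained-only figures would fall too. The 4.9 lb is a two-arm conversion of the stated effect size (2 × 0.245 × 10) that the plan does not itself give. Read as a three-group figure, it corresponds to 2.45 × 3/√2 = 5.2 lb (two equal high-protein arms) or 2 × 2.45 × √1.5 = 6.0 lb (extreme pair, equal spacing).

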Satiety Questionnaire: Satiety will be measured by using a visual analog scale. Participants will be asked to rate the degree to which they felt hungry by placing a mark on a visual analog scale numbered 0 to 10 (0 indicating "not hungry at all" and 10 indicating "as hungry as I have ever felt"). Participants will complete the scales at baseline and weeks 2, 4, 6, 8, 12 and 16.

Dietary Interventions: All participants will receive individual consultation on their respective diet plans, lifestyle modification, and physical activity with a registered dietitian or healthcare provider (i.e. nurse practitioner or physician) throughout the study. At the initial visit patient will not be calorie restricted but will have standardization of their nutritional macronutrient intake based on their group randomization. At the 2 week visit patient will then begin a 1500

calorie restricted diet with the same macronutrient composition (i.e. 30% protein and 40% carbohydrate, and 15% protein and 55% carbohydrate respectively for the high and standard protein groups). Participants in the high protein groups will receive a diet plan based on 1 gram of protein per pound of lean body mass, while the standard protein group will receive 0.5 gram of protein per pound of lean body mass. All subjects will be given guidelines to balance the rest of their caloric and nutritional needs with fruits, vegetables, and whole grains. All participants will meet with a dietitian or healthcare provider at baseline and weeks 2, 4, 6, 8, 12 and 16. Participants will also be weighed at each of these visits and will pick up meal replacement products at that time. All participants will be advised to keep self-monitoring daily food diaries to help with diet compliance and behavior change. Subjects will also be asked to complete the visual analog scale to assess fullness with the overall diet at the same time the 3DFR is being kept. Adherence with strict dietary controls will be performed by reviewing daily patient logs and telephone calls.

vii. Laboratory Studies: Blood samples will be obtained by venipuncture. Subjects will be required to fast at least 8 h and not more than 14 h prior to venipuncture. The laboratory tests will consist of the following: Chemistry Panel, Complete Blood Count (CBC), HbAl c, Lipid Panel, Liver Function Panel, Thyroid Stimulating Hormone (TSH) and C-Reactive Protein (CRP) performed by the laboratory.

Insulin/Glucose: Insulin is measured using a commercial double antibody 1^{125} method. Glucose is measured using spectrophotometry at 505 nm absorbance.

Lipids — Cholesterol, High Density Lipoprotein (HDL) Cholesterol, Triglycerides: Plasma cholesterol and triacylglycerol are determined using standard enzymatic methods. The interassay coefficients of variation are less than 4% and interassay variation is usually less than 2%. These levels of precision are required for the types of nutritional studies carried out by the core in recent years demonstrating statistically significant changes in total cholesterol with adherence to a low fat diet and modest weight loss. Concentrations of alpha cholesterol are determined enzymatically. The alpha cholesterol is derived from the measurement on the supernatant following the precipitation of apo B containing lipoproteins with Heparin and MnCl₂. The so-called low density lipoprotein (LDL) or beta lipoprotein cholesterol is estimated from these data using the Friedenwald equation. For seven years, the laboratory has participated with the Centers for Disease Control in the standardization program for measuring cholesterol, HDL cholesterol and triacylglycerol and it continues to meet the criteria required by the center for disease control in the analyses of these plasma lipids. The laboratory has been assigned a Laboratory I.D. No. LSP 266 for the ODC-NHLB1 Lipid Standardization Program.

viii. Hormonal and Biochemical Assays: The ability to conveniently and rapidly profile a diverse set of peptides has valuable applications. The comparison of a biomarker profile is important both for the better understanding of pathophysiology and for the development of improved clinical diagnostics. In a step toward further enabling such a capability, we propose to utilize a biomarker kit based on Phoenix Pharmaceuticals. This kit is able to measure levels of GLP-1, PYY₃₋₃₆, adiponectin, IGF-1, interleukin (IL)-6, leptin, acyl ghrelin, CCK, gastrin and tumor necrosis factor (TNF)-alpha. We intend to measure leptin, IGF-1, TNF-alpha, and IL-6 concentrations because recent studies have demonstrated a strong positive correlation of serum levels with percentage of body fat.

To assay the levels in hormones that are released in the high protein *versus* standard protein meal, we intend to use the "Obesity Peptide Biomarker Chip" from Phoenix Pharmaceuticals (Appendix 2). From the designed antibodies immobilized on the nitrocellulose coated slide, the results from this assay can qualitatively indicate the concentration of these obesity-related hormones from serum/plasma, adipocytes, or conditioned medium. This kit contains a two-pad glass slide. Each pad has been spotted with 36 to 40 kinds of capture antibodies to detect the corresponding sample antigens. First, the test serum is biotinylated and purified. Following purification, the nonspecific binding sites of the capture antibodies are blocked with blocking

solution. Biotinylated antigens in the sample or in the standard solution can then bind to the capture antibodies immobilized on the nitrocellulose pads. Streptavidin-horseradish peroxidase is added and will subsequently catalyze the chemiluminescence substrate solution. The enzyme-substrate reaction is imaged by CCD camera, chemiluminescence imager, or X-ray film. Spot intensity will be counted and is directly proportional to the amount of antigen in the test sample. A direct comparison between sample and standard will give the biomarker profile in question. After knowing which marker is up or down regulated, the conventional ELISA will be used for accurate quantitation of those biomarkers. We first obtain the baseline of hormone release before starting the meal replacement, at fasting, 1 hour, 2 hour, and 4 hour postprandial time-points. At the first week after initiation of the meal replacement, the subjects repeat the above tests. The test interval is then extended to one month to two months.

ix. Bioelectrical Impedance Analysis (BIA), Hepatic Transient Elastography (Fibroscan) and Anthropomorphic Measurements:

Bioelectrical Impedance Analysis will be obtained at baseline and at weeks 2, 4, 6, 8, 12 and 16 by a physician, nurse practitioner or trained research dietician in our department of gastroenterology at VAGLAHS. This noninvasive tool permits the assessment of both visceral and total fat composition. It is anticipated that this assessment will take approximately 5-10 minutes to complete. The data will be saved using VA equipment to ensure that patient privacy. A visceral/extremity fat content, body fat percentage and basal metabolic rate will be measured. Hepatic Transient Elastography will be obtained at baseline and at weeks 2, 4, 6, 8, 12 and 16 by a certified technician in our department of gastroenterology at VAGLAHS. This noninvasive tool uses ultrasound to characterize the liver stiffness and fat composition of the liver. It is anticipated that this assessment will take approximately 5-10 minutes to complete. The data will be saved using VA equipment to ensure that patient privacy. A liver stiffness score and fat composition will be measured.

Body anthropometry will be performed using the Gulick II 180 centimeter measuring tape with tensiometer (Country Technology, Wisconsin) that will be performed by the nutrition service. The landmark for the waist circumference is approximately below the lowest rib. All measurements will be taken at the end of expiration. Hip circumference will be measured at the maximum extension point around the buttocks. Height will be assessed using a stadiometer and performed in bare feet. Weight will be measured in all subjects using the same scale to ensure standardization.

viii. Fecal Sampling

Stool samples will be collected on day 3, 7, 14, 17, 21, 28, 42, 56, 84 and 112. Subjects will be provided with kits for home sampling. The subjects will urinate first then defecate into the Fisherbrand Commode Specimen Collection System. Subjects will use a spoon to transfer freshly defecated feces to a Para-Pak stool collection cup prefilled with 95% ethanol to fix the samples, allowing storage at room temperature for up to 2 weeks. The remaining feces will be frozen. This involves removing the cup from the toilet hat, tightly closing the lid, and transferring the cup to a Ziploc bag for storage in the subject's freezer. Frozen samples will be delivered to the VA clinic during scheduled study visits using a Styrofoam box and frozen packs. Subjects who forget to bring samples will be provided with prepaid envelopes to mail their samples to the coordinator. Samples will be stored at -80°C. Ethanol-fixed and fresh frozen samples give comparable metagenomics results to samples stored in preservatives such as RNALater while minimizing subjects' risk of exposure to toxic chemicals ⁽³³⁾.

Statistical Analysis:

Statistical Design: This is a 2-group randomized nutritional study to evaluate whether the high-protein diet will improve weight loss in comparison to a standard (control) diet. Eligible subjects will be randomly assigned into one of the two groups in a ratio of 1:1.

Sample Size Determination: The sample size is determined based on the Specific Aim 1 to significantly improve weight loss, as observed by comparing the high-protein diet to the standard diet. The primary outcome of interest is weight loss at 16 weeks (the end of the study). An evaluable sample size of at least 165 (i.e., 55 per arm) will achieve 80% power to detect an effect size of 0.245 using an F test with a two-sided 0.05 significance level when comparing each of the two high-protein diets to the standard diet, assuming that the mean weight loss for the standard diet is 14 lbs with the common standard deviation within group of 10 (from preliminary data), and the size of the variation in the means is 2.45. To account for an attrition rate of up to 20%, we will enroll a total of 200 subjects (66 per arm). Preliminary data suggest that the estimated effect size ranges from 0.23-0.34 when comparing the high-protein diet to the standard diet.

Data Analysis: Descriptive statistics (mean, standard deviation, median, inter-quartile range, and frequency distribution) of demographic information and baseline assessments will be generated to characterize the study participants. Patient characteristics and baseline measurements of the three diet groups will be compared using analysis of variance (ANOVA) for continuous variables, and Chi-square test for categorical variables to evaluate the appropriateness of the randomization. If the distribution of the variable is skewed, an appropriate variable transformation will be made before the comparison. Nonparametric methods, such as Kruskal-Wallis one-way analysis of variance, will also be used for comparison.

Primary Endpoint: the primary endpoint is change in body weight, which is calculated as the difference between Day 1 (baseline) and 16 weeks. The primary objective is to compare the weight loss between the high-protein diet and the standard diet. We will use ANOVA to compare the change in weight among the three groups (through contrast), and also use ANCOVA to compare the weight loss among these groups, adjusting for the baseline values and gender. If the primary endpoint is non-normally distributed, the Kruskal-Wallis one-way analysis of variance will be used.

Secondary Endpoints: The secondary endpoints are (1) efficacy variables: nutrition assessments (FFQ, 3DFR, and satiation questionnaire), anthropometric profiles (e.g., waist and hip circumferences), laboratory and biochemical variables (e.g., insulin, lipid levels, HbA1c), body composition (e.g., body fat), liver stiffness, microbiome changes, and level of hormones; (2) safety variables: incidence, severity and duration of adverse events, vital signs, concomitant medications and physical examination results.

Secondary Statistical Analyses: All analyses will be performed using SAS software (SAS Institute Inc., Cary, NC). First, linear mixed-effects regression model (or GEE model) will be constructed to examine the study effect on the weight loss over time among the two diet plans, referred to as Model 1. Covariates include gender, diet group (high-protein and standard), time that the measurement is taken, and an interaction between diet plan and time. Models also include the subject-level random effects to account for the correlation between repeated measures at baseline and subsequent follow-up visits occurring at 2 week to 1 month intervals. Next, mixed-effects regression models will be used to evaluate the differences in hormonal patterns among the three diet plans for various hormones of interest (e.g., CCK, GLP-1, etc). Since the hormonal level over time is expected to be nonlinear, the covariates in the model include diet group (normal vs. high-protein), time (in days), and smooth-spline function of time by group interaction. Next, we will also construct linear mixed-effects regression models to examine the study effect on the continuous efficacy variables and safety variables (e.g., vital signs) over time among the three diet plans using PROC MIXED. The continuous efficacy variables include nutritional assessments (FFQ, 3DFR, and Satiety), selected laboratory and biochemical variables (e.g., HbA1c, insulin), body fat, etc. Models include the same fixed effects in Model 1, and the subject-level random effects, which account for the correlation between repeated measures at baseline and pre-defined time points for different variables (e.g.,

baseline and at weeks 2, 4, 6, 8, 12 and 16 for the nutritional assessments). Lastly, generalized linear mixed-effect regressions will be used to model *any* dichotomous and categorical (e.g., severity of adverse events) secondary variables, respectively, in the PROC GLIMMIX or GENMOD. All tests will be two-sided, and significance level is $p < 0.05$.

Expected Results/Pitfalls/Significance: We do not anticipate problems in conducting the proposed human experimental studies. Our preliminary data indicate that an isocaloric high protein diet is effective at achieving a reduction in BMI in obese subjects. It is therefore likely that the results will parallel those of the preliminary studies due to the long-term study design and larger study population. It is expected that there is inhibition of the release of ghrelin, which will also be reflected through satiety questionnaires which will be performed during the study.

B. Aim 2. Characterize the changes in the fecal microbiome induced by a high protein diet.

Rationale and hypothesis: Based on our preclinical rodent model data, we hypothesize that a high protein diet will shift the composition of the microbiome of obese subjects, including increased *Akkermansia*, and that this will result in an altered metagenome (abundances of bacterial genes).

Study design: This is a randomized study using the same subjects described in Aim 1. Nutritional assessment, physical examination, bioelectrical impedance, laboratories will be performed at baseline, and weeks 2, 4, 6, 8, 12 and 16. Stool samples will be collected on day 3, 7, 14, 17, 21, 28, 42, 56, 84 and 112.

Study timeline: Data collection will be completed at week 16. The stool samples collected during the study period will be used for 16S rRNA sequencing, shotgun metagenomics, and data analysis.

Fecal sampling: Subjects will be provided with kits for home sampling. The subjects will urinate first then defecate into the Fisherbrand Commode Specimen Collection System. Subjects will use a spoon to transfer freshly defecated feces to a Para-Pak stool collection cup prefilled with 95% ethanol to fix the samples, allowing storage at room temperature for up to 2 weeks. The remaining feces will be frozen. This involves removing the cup from the toilet hat, tightly closing the lid, and transferring the cup to a Ziploc bag for storage in the subject's freezer. Frozen samples will be delivered to the VA clinic during scheduled study visits using a Styrofoam box and frozen packs. Subjects who forget to bring samples will be provided with prepaid envelopes to mail their samples to the coordinator. Samples will be stored at -80°C. Ethanol-fixed and fresh frozen samples give comparable metagenomics results to samples stored in preservatives such as RNALater while minimizing subjects' risk of exposure to toxic chemicals^(70,33).

2.1 Kinetic analysis of shifts in microbial composition in obese subjects (BMI 27-40) on a high protein diet compared to an isocaloric normal protein diet.

Experimental protocol: DNA will be extracted from fecal samples collected in ethanol using the MoBio Powersoil kit. Sequencing of the 254 base pair V4 region of 16S ribosomal DNA will be performed as we previously described using the HiSeq 2500 to a depth of >200,000 reads per sample^(71,34). Microbial diversity will be compared between the two dietary groups at each time point using the Chao1 index, Shannon index, and phylogenetic diversity. Significance will be determined using a two-sided t-test. Microbial composition will be compared across all samples using weighted UniFrac (a phylogenetic distance metric) and principal coordinates analysis. Significance of differences in composition will be determined using Adonis.

Microbial abundance will be compared between baseline data for the two groups to confirm that randomization was effective in abolishing a pre-existing microbial difference between the

